6.9 Adverse Events Assessments

6.9.1 Performing Adverse Event (AE) Assessments

Qualified study staff responsible for assessing AEs will be listed on the Site Authorization and Delegation Log. This includes assessment of AE severity and relationship to the study medication. AE information may be volunteered by the subject or solicited by study personnel through non-leading questions.

All AEs occurring during the study, regardless of the assumption of causal relationship, must be documented on the respective electronic case report form (eCRF). Adverse events should be documented from the time the subject signs the informed consent until the subject's last study visit. If an event occurs during the washout period (prior to subject enrollment and the administration of study medication), it should be recorded as an AE. Any medical condition present prior to administration of the study medication which remains unchanged or improved should not be recorded as an AE at subsequent visits.

If a subject has an ongoing AE at the time of study completion, the ongoing AE must be followed-up and provided appropriate medical care until the event has resolved or stabilized, the subject is lost to follow-up, or there is other resolution to the event.

Documentation of AEs/adverse reactions includes start date and stop date, severity, action(s) taken, seriousness and outcome.

Investigators are also asked to note all observations of new or worsening conjunctival hyperemia on the biomicroscopy eCRF as well as on the study AE form if deemed necessary (per Investigator discretion).

The following definitions of terms apply to this section:

- Adverse event (AE). Any untoward medical occurrence associated with the use of a drug in humans, whether or not considered drug related.
- Suspected adverse reaction (SAR). Any AE for which there is a reasonable possibility that the drug caused the AE. For the purposes of IND safety reporting, “reasonable possibility” means there is evidence to suggest a causal relationship between the drug and the AE. Suspected adverse reaction implies a lesser degree of certainty about causality than adverse reaction, which means any AE caused by a drug.
- Life-threatening AE or life-threatening SAR. An AE or SAR is considered “life-threatening” if, in the view of either the Investigator or Sponsor, its occurrence places the patient at immediate risk of death. It does not include an AE or SAR that, had it occurred in a more severe form, might have caused death.
- Serious adverse event (SAE) or serious suspected adverse reaction (SSAR). An AE or SAR is considered “serious” if, in the view of either the Investigator or Sponsor, it results in any of the following outcomes: Death, a life-threatening AE, patient hospitalization or prolongation of existing hospitalization, a persistent or significant incapacity or substantial disruption of the ability to conduct normal life functions, or a congenital anomaly/birth defect. Important medical events that may not result in death, be life-threatening, or require hospitalization may be considered serious when, based upon appropriate medical judgment, they may jeopardize the patient and may require medical or surgical intervention to prevent one of the outcomes listed in this definition. Examples of such medical events include allergic bronchospasm requiring intensive treatment in an emergency room or at home, blood dyscrasias or convulsions that do not result in patient hospitalization, or the development of drug dependency or drug abuse.
- Unexpected AE or unexpected SAR. An AE or SAR is considered “unexpected” if it is not listed in the Investigator’s Brochure (IB), the Package Insert, or is not listed at the specificity or severity that has been observed. For example, under this definition, hepatic necrosis would be unexpected (by virtue of greater severity) if the IB referred only to elevated hepatic enzymes or hepatitis. Similarly, cerebral thromboembolism and cerebral vasculitis would be unexpected (by virtue of greater specificity) if the IB listed only cerebral vascular accidents. “Unexpected,” as used in this definition, also refers to AEs or SARs that are mentioned in the IB as occurring with a class of drugs or as anticipated from the pharmacological properties of the drug, but are not specifically mentioned as occurring with the particular drug under investigation.

6.9.2 Timing

The AEs occurring during the study must be documented, regardless of the assumption of a causal relationship. AEs should be documented from the time the subject signs and dates the patient consent form until subject participation in the study has been completed. If a subject has one or more ongoing AEs at the time of study completion, the subject should be followed and provided appropriate medical care until the event is resolved or stabilized, the subject is lost to follow-up, or there is other resolution to the event. These follow-up visits will be documented.

When recording an AE, the following information should be provided on the study AE eCRF:

1. Action Taken with Study Medication:

- None
- Study Medication Interrupted
- Study Medication Discontinued

2. Other Action Taken:

- None
- Non-Drug Therapy
- New OTC or Rx Drug Added
- Hospitalized less than 24 hours
- Hospitalized greater than or equal to 24 hours

3. Outcome of an adverse event is coded as:

- Fatal
- Not Recovered/Not Resolved
- Recovered/Resolved
- Recovered/Resolved with sequelae
- Recovering/Resolving
- Unknown/Lost to follow-up

6.9.3 Severity

Severity of an AE is defined as a qualitative assessment of the level of discomfort or the degree of intensity of an AE as determined by the Investigator or reported to him/her by the subject. The assessment of severity is made irrespective of study medication relationship or seriousness of the event and should be evaluated according to the following scale:

1 = Mild: present and noticeable, but not distressing, and no disruption of normal daily activities.

2 = Moderate: bothersome, discomfort sufficient to possibly reduce or affect normal daily activity.

3 = Severe: incapacitating, with inability to work or perform normal daily activity.

A change in increased severity for a reported AE will require a stop date for the previous severity and a new start and stop date for the new severity. For example, a change in severity may go from mild to severe or from moderate to severe. In both cases, the start and stop dates should be recorded.

Note: A severe AE is not the same as a serious AE. Seriousness of an AE (NOT severity) serves as a guide for defining regulatory reporting obligations (see Section [6.9.6](#) for further information on serious AEs [SAEs]).

6.9.4 Relationship

The study medication relationship for each AE/adverse reaction should be determined by the Investigator using these explanations:

- **Not Related:** The event is clearly related to other factors such as subject's clinical condition; therapeutic interventions, concomitant disease or therapy administered to the subject and does not follow a known response pattern to the product.
- **Unlikely Related:** The event is most probably caused by other etiologies such as participant's underlying condition, therapeutic intervention, or concomitant therapy; or the delay between administration and the onset of the AE is incompatible with a causal relationship. Therefore, there is not a reasonable possibility that the AE was caused by the study medication.
- **Possibly Related:** The event follows a reasonable, temporal sequence from the time of study medication administration and/or follows a known response pattern to the study medication, but could have been produced by other factors such as the subject's clinical state, therapeutic interventions or concomitant therapy administered to the subject.
- **Related:** The event follows a reasonable, temporal sequence from the time of study medication administration and/or follows a known response pattern to the study

medication and cannot be reasonably explained by other factors such as subject's clinical state, therapeutic interventions or concomitant therapy administered to the subject, and either occurs immediately following study medication administration, or improves on stopping the study medication, or reappears on repeat exposure, or there is a positive reaction at the application site.

6.9.5 Expectedness

An AE or suspected adverse reaction is considered "unexpected" if it is not listed in the IB or is not listed at the specificity or severity that has been observed. "Unexpected," as used in this definition, also refers to adverse events or suspected adverse reactions that are mentioned in the IB as occurring with this class of drugs or as anticipated from the pharmacological properties of netarsudil, and are not specifically mentioned as occurring with the study medication. The AEs and adverse reactions that are both unexpected and serious should be reported in an expedited fashion to the Sponsor (see Section 6.9.6 for further details).

6.9.6 Serious Adverse Events, Suspected Serious Adverse Reactions or Suspected Unexpected Serious Adverse Reactions

6.9.6.1 Reporting SAEs, SSARs or SUSARs

An Investigator must immediately (i.e., within 24 hours) report any SAE, SSAR or SUSAR to the Sponsor using the SAE report form, whether or not considered medication-related, including those listed in the IB, and must include an assessment of whether there is a reasonable possibility that the medication caused the event. In addition, in the case of immediately life-threatening AEs or AEs with fatal outcome, or SUSARs, the Investigator must inform the Sponsor by phone within 24 hours of observation or occurrence of the SAE.

The Investigator must report any SAE, SSAR, or SUSAR that occurs during the course of the study or within 4 weeks of last study visit. In case of incomplete information, the Investigator must provide follow-up information as soon as possible, again using the SAE report form.

SAEs, SSARs, and SUSARs must be reported to the IRB/IEC according to the IRB/IEC requirements.

The contact information of the study Safety Mailbox is as follows:

Covance PSS
[contact]
[contact]

The contact information of the study Medical Monitors is as follows:

[name]
[contact]
Email: [contact]

6.9.7 Pregnancy Reporting

Pregnancies occurring in subjects in this study, occurring up to the subject's last study visit, must be reported and followed to outcome. Information on pregnant partners will not be collected.

While pregnancy itself is not considered to be an AE or SAE, pregnancy reports are tracked by Covance and the study Medical Monitor. Premature terminations including miscarriage, spontaneous abortion, or elective termination of a pregnancy for medical reasons will be reported as an SAE. Other pregnancy complications should be reported as SAEs, if they meet serious criteria. Should a pregnancy result in a congenital anomaly or birth defect, a separate SAE report must be submitted for the baby. Furthermore, all neonatal deaths that occur within 30 days of the birth should be reported as SAEs, without regard to causality.

The Investigator must complete the pregnancy report form and email the form to the study Safety Mailbox within 1 business day of knowledge of the pregnancy. Following delivery or termination of pregnancy, the updated or follow-up pregnancy report form is to be completed and submitted by fax or email to the Safety Mailbox for the study.

6.10 Removal of Subjects from the Study or Study Medication

Subjects may be discontinued from the study at any time for any reason. Participation is entirely voluntary, and only possible if the subject has signed informed consent. Consent may be withdrawn at any time.

6.10.1 Completed Subject

A completed subject is defined as one who completes all planned study treatments and visits.

6.10.2 Non-completing Subject

A non-completing subject is defined as one who exits the study by their own volition or at the discretion of the Investigator, the Medical Monitor, and/or an Aerie Safety Officer/designee. Any subject may decide to voluntarily withdraw from the study at any time without prejudice. If discontinuation of treatment is necessary, the Investigator will make every attempt to complete all subsequent safety assessments listed for the Week 8 / Early Termination Visit.

The subject may also be discontinued from the study for the following reasons:

- AEs (including intercurrent diseases reported by the subject or observed by the Investigator with documentation on the CRF)
- Withdrawal of Consent
- Non-compliance (e.g., non-adherence to scheduled follow-up visits or use of study treatment)

- Lost to Follow-up
- Pregnancy
- Investigator Decision
- Protocol Deviation
- Death
- Other

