9.1.2 Missing Data and Intercurrent Events

The primary analysis will be completed with available data per subject from the mITT population. Robustness analyses will also be presented based on the multiple imputation methodology under different assumptions of missingness and intercurrent events (at random and not at random), using last observation carried forward (LOCF), and using the per protocol population with available data per subject.

Intercurrent events will be primarily handled in the following manner:

1. Discontinuation of study medication and non-optimal compliance will be ignored, values measured after discontinuation of study medication or regardless of compliance will be used in the analyses [treatment policy strategy].
2. Withdrawal due to lack of efficacy or adverse events: missing data will be singly imputed as the worst within subject observation prior to the intercurrent event [hypothetical strategy].
3. Missing data without withdrawal or withdrawal due to reasons other than lack of efficacy or adverse events: missing data will be imputed employing Multiple Imputation (MI) using randomized treatment-based Markov Chain Monte Carlo (MCMC) methodology to impute non-monotone missing data and regression methodology to impute monotone missing data [hypothetical strategy].

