### **8.2 Missing or Inconclusive Data Handling**

#### **8.2.1 ASSESSMENT WINDOWS**

Assessment window mapping will be applied to both efficacy and safety outcomes for table summaries using observed data only (ODO). Unscheduled or early termination visits that are within the protocol specified window of a scheduled visit will be mapped to that visit to replace the missing scheduled visit. Missing data handling for efficacy variables as described in Section 8.2.2 will be applied after assessment window mapping. Both the actual visit and windowed visit will be displayed in the listings.

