#### **8.2.2 MISSING DATA HANDLING FOR EFFICACY VARIABLES**

The primary analysis will be completed with available data per subject from the mITT population.

Robustness analyses will also be presented based on the multiple imputation (MI) methodology under different assumptions of missingness and intercurrent events, using last observation carried forward (LOCF), and using the PP population with available data per subject. Imputation using MI or LOCF will

only be performed on study eye missing data at post-baseline scheduled visits. No imputation will be performed for missing fellow eye data and unscheduled post-baseline visits.

Intercurrent events will be primarily handled in the following manner:

1. Discontinuation of study medication and non-optimal compliance will be ignored, values measured after discontinuation of study medication or regardless of compliance will be used in the analyses [treatment policy strategy].
2. Withdrawal due to lack of efficacy or AEs: missing data will be singly imputed as the worst within subject observation prior to the intercurrent event [hypothetical strategy]. For efficacy variable CCT, the worst is the maximum within subject observations. In addition, the worst observation should come from post-baseline scheduled and unscheduled visits prior to the intercurrent event.
3. Missing data without withdrawal or withdrawal due to reasons other than lack of efficacy or AEs: missing data will be imputed employing MI fully conditional specification (FCS) regression method.

For the LOCF imputation, only the observations from post-baseline visits including scheduled, unscheduled, and early termination visits for a given subject will be carried forward.

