#### Two-sample t-test for comparison between treatments:

```
proc ttest data = indata;
  class treatment;
  var CHG_CCT;
```

```
run;
```

Wilcoxon rank sum test for comparison between treatments:

```
proc npar1way data = indata wilcoxon;
  class treatment;
  var CHG_CCT;
run;
```

ANCOVA model for modeling the treatment effect:

```
proc mixed data = indata;
  class treatment;
  model CHG_CCT = treatment baseline_CCT;
  lsmeans treatment / cl pdiff;
run;
```

The primary analysis will use the mITT population with available data per subject at eye level (ie, ODO). Robustness analyses (details provided in Section 8.2.1) will also be presented based on the MI methodology under different assumptions of missingness and intercurrent events (where missing data or withdrawal due to lack of efficacy or AEs will be imputed using FCS regression method and missing data for all other reasons will be imputed using worst within subject observation prior to the intercurrent event).

Missing data handling using MI under different assumptions of missingness and intercurrent events are described in steps along with example SAS® code for the primary analyses one-sample t-test and two-sample t-test.

Step 1: Imputation step

The following SAS® code will be employed to produce twenty “complete” (imputed) datasets using MI FCS methodology:

```
proc mi data = indata (where (seye = eye)) seed = 999 out = outdata1
nimpude = 20;
  class treatment;
  var treatment baseline_CCT aval2 aval4 aval8;
  fcs;
run;
```

where

- `indata` is the name of the input dataset
- `outdata1` is the name of the output dataset;
- `treatment` is the treatment group variable;
- `baseline_CCT` is the baseline mean CCT value; and
- `aval2`, `aval4`, and `aval8` are the mean CCT values at Week 2, Week 4, and Week 8, respectively.

Step 2. Finalization of imputed datasets from MI under different assumptions of missingness and intercurrent events

After obtaining twenty “complete” datasets, for subjects with withdrawal due to lack of efficacy or AEs, the imputed missing values in each dataset will be replaced by the worst within subject observation from post-baseline visits (including both scheduled and unscheduled visits) prior to the intercurrent event. After replacement, change from baseline mean CCT (CHG\_CCT) will be calculated all post-baseline visits in each dataset.

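### The plan promises to use CCT values measured after study drug is stopped, but nothing tells sites to collect them at the scheduled visits

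*Protocol*

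**What the plan says.** **Estimand.** Protocol 9.1.2, repeated in 9.8.2, labels drug discontinuation and poor compliance as treatment policy: "values measured after discontinuation of study medication or regardless of compliance will be used in the analyses". SAP 8.2.2 carries the rule over: "Discontinuation of study medication and non-optimal compliance will be ignored, values measured after discontinuation of study medication" are to be used.

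**Primary data set.** Protocol 9.1.2: "The primary analysis will be completed with available data per subject from the mITT population". SAP 12.2 is more explicit: "The primary analysis will use the mITT population with available data per subject at eye level (ie, ODO"), that is, observed data only, with no imputation.

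**Follow-up after stopping.**
- Protocol 6.10.1: "A completed subject is defined as one who completes all planned study treatments and visits". A subject who stops drops early is therefore not a completer.
- Protocol 6.10.2 deals with stopping treatment under the heading for non-completing subjects, whom it defines as those who exit the study. If treatment is discontinued, the investigator is to "make every attempt to complete all subsequent safety assessments listed for the Week 8 / Early Termination Visit". Its list of reasons for discontinuing a subject from the study includes "Non-compliance (e.g., non-adherence to scheduled follow-up visits or use of study treatment").
- Protocol 6.10.3 requires medical follow-up after a stop for an adverse event and does not mention CCT. After consent withdrawal or discontinuation for non-compliance, it seeks one final visit with every Week 8/Early Termination examination. That list (7.2.4) includes CCT.

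**Visit mapping.** Under SAP 8.2.1, unscheduled or early-termination visits "within the protocol specified window of a scheduled visit will be mapped to that visit".

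**The concern.** A treatment-policy analysis of Week 4 CCT needs a Week 4 CCT from every subject, whatever has happened to dosing. The statistical sections assume those values will exist. The conduct sections do not ask for them, and the only request specific to stopping treatment names safety assessments. About 20 sites are left to decide for themselves.

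If sites follow 6.10.2 literally, some subjects who stop before Week 4 will have no Week 4 value and will fall out of the primary test. If they stop because of intolerance or lack of effect, the reported mean change would be more favourable than the stated estimand. Protocol 9.3 says the study is meant to inform the design and power of later trials, so an inflated mean change would carry forward.

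**Working it through.** **Step 1. Is CCT covered by a request for safety assessments?** The safety lists (Protocol synopsis, SAP 2.2) contain adverse events, BCVA, biomicroscopy, ophthalmoscopy, vital signs and IOP. CCT is not among them; it sits under efficacy (Protocol 6.7.1). So 6.10.2 covers BCVA at the exit visit but not CCT.

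**Step 2. When does an exit CCT count?** The Week 4 window is Day 28 ± 3, or Day 25 to 31. A subject who stops around Week 2 and has an exit visit then has no Week 4 value.

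**Step 3. Who is affected?** For the primary endpoint, only subjects who stop before Week 4 and have no CCT on Day 25 to 31. Later stoppers affect only the Week 8 secondary endpoints.

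**Step 4. Where do the missing subjects reappear?** Only in the Week 4 robustness tables: 14.2.1.2 (multiple imputation) and, if they have a post-baseline value, 14.2.1.3 (LOCF). Both fill the gap by imputation or carry-forward, not with an observed off-drug value.

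**Step 5. The plan's own figure.** Inputs from Protocol 9.3: mean change 34.6 µm, SD 60 µm, n = 20 per group, one-sample t-test, two-sided alpha 0.10. Effect size 34.6/60 = 0.577. Exact power from the non-central t (19 df, non-centrality 0.577 × √20) is 0.8001, matching the stated 80%.

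**Step 6. Size of the gap.** Let m = 34.6 µm be the mean reduction in those measured, p the fraction who stop before Week 4 unmeasured, and r the share of the effect that stoppers retain. Both p and r are assumptions.

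- Observed-data mean = m
- Treatment-policy mean = m(1 − p) + r·m·p
- Gap = m·p·(1 − r)

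| p | r | Treatment-policy mean (µm) | Gap (µm) |
|---|---|---|---|
| 10% | 0 | 34.6 × 0.90 = 31.1 | 34.6 × 0.10 = 3.5 |
| 20% | 0 | 34.6 × 0.80 = 27.7 | 34.6 × 0.20 = 6.9 |
| 10% | 0.5 | 34.6 × 0.95 = 32.9 | 34.6 × 0.05 = 1.7 |
| 20% | 0.5 | 34.6 × 0.90 = 31.1 | 34.6 × 0.10 = 3.5 |

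**Step 7. Does power bear on the point?** Leaving stoppers out gives n = 18 or 16 and power 0.759 or 0.711 at effect size 0.577. Measuring all 20 with r = 0 lowers the mean to 31.1 or 27.7 µm and raises the SD, √(60² + p(1 − p) × 34.6²), to 60.9 or 61.6 µm. Power is then 0.712 or 0.615. With r = 0.5 it is 0.760 or 0.718.

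**The case against.** The strongest reply is that the protocol is silent rather than restrictive. CCT is due at every visit (6.7.1, Table 1), and nothing ends the visits when drops stop. The heading of 6.10 distinguishes removal from the study and from study medication. The adverse event form has its own entry for stopping study medication (6.9.2), and SAP 13.1 reports that outcome apart from the study-discontinuation reasons in SAP 9. Non-adherence is a reason why a subject may be discontinued, not an automatic exit. Section 6.10.3 also seeks CCT from those discontinued for non-compliance.

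All of this stands, and it limits the point to a missing instruction. It does not remove it: the text written for the moment treatment stops asks for less than the estimand needs, and one exit visit seldom supplies a Week 4 value for an early stopper.

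Four stronger readings are tempting, and the documents do not support them.
- A reader might infer that the protocol stops CCT measurement once drops stop. No section says so.
- A reader might infer that the primary result is a mean over on-drug completers. It is not: poor compliers, subjects off drug who attend Week 4, in-window exit visits and anyone leaving after Week 4 all stay in.
- A reader might infer that lost power is a reason to act. Step 7 shows otherwise: if stoppers keep no effect, measuring them lowers power, and if they keep half, it hardly changes. Only the bias argument supports the change.
- A reader might infer that the worst-value rule for withdrawals conflicts with the observed-data test. SAP 12.2 (Step 2) and the titles of Tables 14.2.1.1 and 14.2.1.2 largely show that this rule and multiple imputation belong to the robustness analysis.

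**Conclusion.** The mismatch is real and limited. The plan states a treatment-policy strategy for stopping study drug, and its conduct sections do not secure the Week 4 CCT values which that strategy requires. Subjects who stop before Week 4 without a CCT on Day 25 to 31 are missing from the primary test.

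The size is conditional. With 10% to 20% of a group stopping early and unmeasured, the observed-data mean exceeds the treatment-policy mean by 3.5 to 6.9 µm if no effect is retained, and by 1.7 to 3.5 µm if half is. The gap is zero if all of the effect is retained or if sites measure these subjects anyway. The documents supply neither a stopping rate nor an off-drug CCT course, so the actual bias cannot be determined from them. Its sign is not assured either: the Protocol introduction notes that reticular oedema seen with netarsudil typically resolves after stopping, so an off-drug CCT need not be the worse one.

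**What to change.** Reconcile Protocol 6.10.2 and 6.10.3 with 9.1.2:
- Separate having stopped study medication from having left the study.
- State that subjects who stop drops but still consent have CCT and BCVA measured at their remaining scheduled visits.
- State that non-adherence to drops does not by itself end data collection.

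This concerns data collection only; when or why treatment is stopped is unchanged. If the sponsor does not want to continue these visits, the treatment-policy label in 9.1.2, 9.8.2 and SAP 8.2.2 should be changed to describe what will be analysed.

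The cost is protocol wording. The visits and measurements are already in Table 1, and the downside is a few off-drug visits.
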